## **6.6 Dose escalation and dose modification**

Study drug dose adjustments and/or interruptions are not permitted.

Any interruption of study drug administration should be discussed with Novartis or delegate regarding the participant's eligibility to continue investigational treatment.

Any missed or altered study drug administration must be recorded on the appropriate eCRF in order to reconstruct an accurate dosing history for each participant.

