### **6.6.1 Dose modifications**

Not applicable

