## 9 Discontinuation and completion

### 9.1 Discontinuation from study treatment and from study

#### 9.1.1 Discontinuation from study treatment

Discontinuation of study treatment for a participant occurs when study treatment is stopped earlier than the protocol planned duration and can be initiated by either the participant or the investigator.

The investigator must discontinue study treatment for a given participant if he/she believes that continuation would negatively impact the participant's well-being.

Study treatment must be discontinued under the following circumstances:

- Participant/guardian decision
- AEs for which continued exposure to the study drug would be detrimental
- Abnormal renal laboratory results requiring discontinuation (see [Section 16.3](#))
- Abnormal liver laboratory results requiring discontinuation (see [Section 16.2](#))
- Platelets < 75000/ $\mu$ L
- Pregnancy (see [Section 5](#) and [Section 8.4.3](#))
- Participant develops a medical condition that requires use of prohibited treatment as per [Section 6.2.2](#) or if participant exhibits a behavior of non-compliance regarding prohibited medications
- Participant experiences a life-threatening hypersensitivity event due to any reason needing an ICU admission or intubation
- Participant experiences a serious hypersensitivity event suspected to be related to study treatment
- Any other protocol deviation that results in a significant risk to the participant's safety
- Any situation in which study participation might result in a safety risk to the participant
- Following emergency unblinding

If discontinuation of study treatment occurs, the investigator should make a reasonable effort to understand the primary reason for the participant's premature discontinuation of study treatment and record this information. The investigator must also contact the IRT to register the participant's discontinuation from study treatment.

Participants who discontinue from study treatment should be encouraged to return for all upcoming visits indicated in the Assessment Schedule ([Table 8-1](#)).

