## 16.2 Appendix 2: Liver event and laboratory trigger definitions & follow-up requirements

**Table 16-2 Liver event and Laboratory trigger definitions**

	Definition/ threshold
Liver laboratory triggers If ALT, AST and total bilirubin normal at baseline:	
 
· ALT or AST > 5 × ULN
 
· ALP > 2 × ULN (in the absence of known bone pathology)
 
· Total bilirubin > 3 × ULN (in the absence of known Gilbert syndrome)
 
· ALT or AST > 3 × ULN and INR > 1.5
 
· Potential Hy's Law cases (defined as ALT or AST > 3 × ULN and Total bilirubin > 2 × ULN [mainly conjugated fraction] without notable increase in ALP to > 2 × ULN)
 
· Any clinical event of jaundice (or equivalent term)
 
· ALT or AST > 3 × ULN accompanied by (general) malaise, fatigue, abdominal pain, nausea, or vomiting, or rash with eosinophilia
 
· Any adverse event potentially indicative of a liver toxicity*
 

If ALT or AST abnormal at baseline:	
 
· ALT or AST > 2x baseline or > 300 U/L (whichever occurs first)
 

*These events cover the following: hepatic failure, fibrosis and cirrhosis, and other liver damage-related conditions; non-infectious hepatitis; benign, malignant and unspecified liver neoplasms ULN: upper limit of normal
	

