**Table 16-3 Follow up requirements for liver laboratory triggers**

	ALT	TBL	Liver Symptoms	Action
ALT increase without bilirubin increase:				
	
If normal at baseline: ALT > 3 x ULN
 
If elevated at baseline: ALT > 2 x baseline or > 300 U/L (whichever occurs first)
	
Normal
 
For participants with Gilbert's syndrome: No change in baseline TBL
	None	
 
• No change to study treatment
 
• Measure ALT, AST, ALP, GGT, TBIL, INR, albumin, CK, and GLDH in 48-72 hours.
 
• Follow-up for symptoms.
 

	
If normal at baseline: ALT > 5 x ULN for more than two weeks
 
If elevated at baseline: ALT > 3 x baseline or > 300 U/L (whichever occurs
	
Normal
 
For participants with Gilbert's syndrome: No change in baseline TBL
	None	
 
• Interrupt study drug
 
• Measure ALT, AST, ALP, GGT, TBIL, INR, albumin, CK, and GLDH in 48-72 hours.
 

	ALT	TBL	Liver Symptoms	Action
	first) for more than two weeks			
 
Follow-up for symptoms.
 
Initiate close monitoring and workup for competing etiologies.
 
Study drug can be restarted only if another etiology is identified and liver enzymes return to baseline.
 

	If normal at baseline: ALT > 8 x ULN	Normal	None	
ALT increase with bilirubin increase:				
	If normal at baseline: ALT > 3 x ULN	TBL > 2 x ULN (or INR > 1.5) For participants with Gilbert's syndrome: Doubling of direct bilirubin	None	
	If elevated at baseline: ALT > 2 x baseline or > 300 U/L (whichever occurs first)			
	If normal at baseline: ALT > 3 x ULN	Normal or elevated	Severe fatigue, nausea, vomiting, right upper quadrant pain	
	If elevated at baseline: ALT > 2 x baseline or > 300 U/L (whichever occurs first)			

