**Table 16-4 Follow up requirements for liver laboratory triggers**

Criteria	Actions required	Follow-up monitoring
Total Bilirubin (isolated)		
>1.5 – 3.0 ULN	
 
Maintain treatment
 
Repeat LFTs within 48-72 hours
 
	Monitor LFTs weekly until resolution c to ≤ Grade 1 or to baseline
> 3 - 10 × ULN (in the absence of known Gilbert syndrome)	
 
Interrupt treatment
 
Repeat LFT within 48-72 hours
 
Hospitalize if clinically appropriate
 
Establish causality
 
Record the AE and contributing factors (e.g. conmeds, med hx, lab) in the appropriate CRF
 
	Monitor LFTs weekly until resolution c to ≤ Grade 1 or to baseline (ALT, AST, total bilirubin, Alb, PT/INR, ALP and GGT) Test for hemolysis (e.g. reticulocytes, haptoglobin, unconjugated [indirect] bilirubin)
> 10 x ULN	
 
Discontinue the study treatment immediately
 
Hospitalize the participant
 
Establish causality
 
Record the AE and contributing factors (e.g. conmeds, med hx, lab) in the appropriate CRF
 
	ALT, AST, total bilirubin, Alb, PT/INR, ALP and GGT until resolution c (frequency at investigator discretion)

Criteria	Actions required	Follow-up monitoring
Any AE potentially indicative of a liver toxicity*	
 
• Consider study treatment interruption or discontinuation
 
• Hospitalization if clinically appropriate
 
• Establish causality
 
• Record the AE and contributing factors (e.g., conmeds, med hx, lab) in the appropriate CRF
 
	Investigator discretion

cResolution is defined as an outcome of one of the following: (1) return to baseline values, (2) stable values at three subsequent monitoring visits at least 2 weeks apart, (3) remain at elevated level after a maximum of 6 months, (4) liver transplantation, and (5) death.
 
*These events cover the following: hepatic failure, fibrosis and cirrhosis, and other liver damage – related conditions; non-infectious hepatitis; the benign, malignant and unspecified liver neoplasms.
		

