### 16.3 Appendix 3: Specific Renal Alert Criteria and Actions and Event Follow-up

**Table 16-5 Specific renal alert criteria and actions**

Renal Event	Actions
Confirmed serum creatinine increase 25% – 49%	
 
• Consider causes and possible interventions
 
• Follow up within 2-5 days
 

Serum creatinine increase $\geq 50\%$ * OR if <18 years old, eGFR $\leq 35\text{mL}/\text{min}/1.73\text{ m}^2$	
 
• Consider causes and possible interventions
 
• Repeat assessment within 24-48h if possible
 
• Consider drug interruption or discontinuation unless other causes are diagnosed and corrected
 
• Consider participant hospitalization and specialized treatment
 

New onset dipstick proteinuria $\geq 3+$ OR Protein-creatinine ratio (PCR) $\geq 1\text{g/g}$ Cr (or mg/mmol equivalent as converted by the measuring laboratory)	
 
• Consider causes and possible interventions
 
• Assess serum albumin & serum protein
 
• Repeat assessment to confirm
 
• Consider drug interruption or discontinuation unless other causes are diagnosed and corrected
 

New onset hematuria $\geq 3+$ on urine dipstick	
Assess & document
 
 
• Repeat assessment to confirm
 
• Distinguish hemoglobinuria from hematuria
 
• Urine sediment microscopy
 
• Assess sCr
 
• Exclude infection, trauma, bleeding from the distal urinary tract/bladder, menstruation
 
• Consider bleeding disorder
 

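### Protocol Section 6.6 bars study drug interruptions that the liver tables order, and the AST-based triggers of Table 16-2 have no action row of their own

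*Protocol*

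**What the plan says.** **Interruption.** Protocol Section 6.6 opens with "Study drug dose adjustments and/or interruptions are not permitted". It continues: "Any interruption of study drug administration should be discussed with Novartis or delegate regarding the participant's eligibility to continue investigational treatment". A third sentence asks for missed or altered administrations to be recorded. Section 6.6.1, on dose modifications, reads "Not applicable".

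Section 16.2 takes a different line. Table 16-3 orders study drug to be interrupted when ALT stays above 5 x ULN for more than two weeks (normal baseline), or above its elevated-baseline equivalent. It then adds "Study drug can be restarted only if another etiology is identified and liver enzymes return to baseline". Table 16-4 orders interruption for isolated total bilirubin above 3 to 10 x ULN. Section 10.2.1 lists interruption among the options after a confirmed liver elevation, Table 16-5 does so for renal events, and Section 10.1.1 lists it as an action taken for an adverse event.

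**AST.** Table 16-2 words its aminotransferase triggers as ALT or AST, for example "Potential Hy's Law cases (defined as ALT or AST". Section 10.2.1 sends sites to Tables 16-3 and 16-4 for the actions.

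**Renal.** Section 9.1.1 includes among the mandatory stops "Abnormal renal laboratory results requiring discontinuation" and points to Section 16.3. The nearest wording in Table 16-5 there is "Consider drug interruption or discontinuation unless other causes are diagnosed and corrected".

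**The concern.** An investigator with a raised liver result may find a flat bar on interruption in the treatment section and an instruction to interrupt in the appendix. An investigator whose participant meets a Table 16-2 trigger through AST will look for an action row and not find one. Two sites could then handle the same result differently.

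This is first a safety-conduct matter, but it also reaches the primary endpoint. SAP Section 1.2.1 scores a participant as a non-responder after treatment discontinuation or more than one missed dose before Week 12. Protocol Section 9.1.1 bars further food challenges after discontinuation. Protocol Section 8.3.1 bars the Week 12 challenge if the Week 12 dose is not given. Whether a result leads to a hold, a stop or continued dosing can therefore decide whether the participant is challenged at all.

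**Working it through.** The plan gives no figure to reproduce here, so the check is textual, followed by a small calculation of size.

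**1. Interruption.** The restart condition in Table 16-3 shows that a temporary hold is meant, not a stop. Two table actions (Tables 16-3 and 16-4) order a hold, and one sentence in Section 6.6 forbids it. The second sentence of 6.6 foresees that interruptions will happen and routes them to the sponsor, but does not say when one is allowed. Section 10.1.1 sharpens the conflict: it rules out dose increases and reductions yet lists interruption as a recordable action, whereas 6.6 rules out both.

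**2. AST triggers against action rows.**

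| Table 16-2 trigger that AST alone can meet | Nearest row | Row entered by |
|---|---|---|
| Above 5 x ULN, normal baseline | Table 16-3, above 5 x ULN for over two weeks | ALT |
| Above 3 x ULN with INR above 1.5 | Table 16-3, above 3 x ULN with bilirubin above 2 x ULN or INR above 1.5 | ALT |
| Potential Hy's Law | Same row | ALT |
| Above 3 x ULN with symptoms | Table 16-3, above 3 x ULN with liver symptoms | ALT |
| Abnormal baseline: above 2 x baseline or 300 U/L | Table 16-3, same thresholds | ALT |

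That is 4 + 1 = 5 triggers and 0 rows entered by AST. Table 16-4 is entered by isolated bilirubin or by a liver-toxicity adverse event. In both tables AST appears only as a test to repeat or monitor.

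**3. Renal.** The liver pointer in Section 9.1.1 does lead to a stop, because Table 16-4 orders immediate discontinuation above 10 x ULN. The renal pointer leads only to the conditional wording of Table 16-5.

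**4. Link to Week 12.** Three doses fall before Week 12: Day 1, Week 4 and Week 8. Table 8-1 schedules one chemistry sample after Day 1 and before Week 12, at Week 4. Suppose the Week 4 dose is given before that result returns. A hold over Week 8 then costs one dose, which is not an intercurrent event, and the participant is still challenged if the Week 12 dose is given. If the hold runs into Week 12 there is no challenge. Permanent discontinuation gives a non-responder.

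**5. Size of one changed classification.** The arm sizes come from SAP Section 3.1.
- Reduced trial: 1/46 = 2.2% of a ligelizumab arm; 1/23 = 4.3% of placebo.
- Planned trial: 1/108 = 0.9%; 1/54 = 1.9%.

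**The case against.** The strongest reply is that Section 6.6, read as a whole, expects interruptions and sends them to the sponsor, so its first sentence is a general rule beside specific safety rules in Sections 16.2 and 16.3. That is a sensible reading, but the text does not state it, and a site reading the first sentence alone would be misled.

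Several stronger inferences are tempting, and the documents do not support them:

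- **Sites must stop treatment for good because holds are barred.** The second sentence of 6.6 contemplates continuing after an interruption. Section 8 says missed visits should not lead automatically to discontinuation, and interruption is not on the mandatory-stop list in 9.1.1.
- **AST-driven cases have no rules, or only discretionary ones.** Section 10.2.1 calls for repeat tests, and for close observation if the elevation is confirmed. Section 9.1.1 requires a stop where continuing would harm the participant. The last row of Table 16-4 covers liver-toxicity adverse events. The gap is an omission, not a contradiction.
- **An AST-driven potential Hy's Law case with bilirubin of 2 to 3 x ULN is told "Maintain treatment".** That row is headed as isolated bilirubin, and bilirubin raised together with AST is not isolated.
- **Table 16-3 conflicts with Table 16-2 on ALT of 3 to 5 x ULN.** Its action there is unchanged treatment with repeat tests and symptom follow-up, which is extra monitoring below the standalone trigger.
- **The renal passages contradict each other.** Section 9.1.1 can be read as covering results for which the Table 16-5 assessment ends in discontinuation. The wording is loose.

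The blank action cells in the lower rows of Table 16-3 may be merged cells lost in reading the PDF, and nothing here relies on them.

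**Conclusion.** The conflict between Section 6.6 and Tables 16-3 and 16-4 is real: one passage forbids what the others order, and no exception links them. The missing AST rows are a real but softer gap, since general provisions still apply. The renal wording is a lesser inconsistency.

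The practical size is small. The documents give no rate of liver or renal triggers. Exclusion criterion 17 removes participants with AST or ALT above 1.5 x ULN at Screening Visit 1, and little scheduled chemistry falls between first dose and Week 12. The recruitment halt and shortened treatment described in SAP Section 1.1 reduce the remaining exposure. For each participant affected, the effect on an arm's responder rate is at most the 2.2 or 4.3 percentage points shown above (46 and 23 per arm), and it occurs only if the choice of passage changes the outcome from responder to non-responder. The finding assumes that the visible table rows are complete as to their entry criteria.

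**What to change.** Three wording changes to the protocol:

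1. Make Section 6.6, Sections 10.1.1 and 10.2.1, and Tables 16-3, 16-4 and 16-5 state one position on interruption for safety reasons, including when it applies.
2. Map each AST-based trigger of Table 16-2 to an action row in Table 16-3 or 16-4.
3. Make the renal item in Section 9.1.1 and the wording of Table 16-5 agree.

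The sponsor decides which clinical rule stands; this review takes no position on that. The cost is text and table edits. No tests are added, because AST, ALT, bilirubin and creatinine are already in the scheduled laboratory panels and INR is already in the coagulation panel and the liver follow-up.

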### **6.6.1 Dose modifications**

Not applicable

## **6.7 Additional treatment guidance**

### **6.7.1 Treatment compliance**

Participants will receive two injections SCq4w at 14 visits during the treatment period. Compliance is assured as long as the participant attends all study visits according to the Schedule of Assessments ([Table 8-1](#)). Study drug is administered at the site only at designated study visits. The administration of study drug must be recorded in the source documents and the corresponding eCRF.

### **6.7.2 Recommended treatment of adverse events**

Any treatment deemed necessary by the investigator for the safety of the participant is allowed. For treatment of severe allergic reactions including anaphylaxis, epinephrine and SABA are typically used.

Treatments of adverse events should align with prohibited medication ([Section 6.2.2](#), [Table 6-3](#)) and medications allowed under certain conditions ([Section 6.2.1.1](#), [Table 6-2](#)). Medication used to treat adverse events (AEs) must be recorded on the appropriate CRF.

For adverse events associated with the DBPCFC, please consult [Section 16.4](#).

### **6.7.3 Emergency breaking of assigned treatment code**

Emergency code breaks must only be undertaken when it is required to in order to treat the participant safely. Most often, study treatment discontinuation and knowledge of the possible treatment assignments are sufficient to treat a study participant who presents with an emergency condition. Emergency treatment code breaks are performed using the IRT. When the investigator contacts the system to break a treatment code for a participant, he/she must provide the requested participant identifying information and confirm the necessity to break the treatment code for the participant. The investigator will then receive details of the investigational drug treatment for the specified participant and a fax or email confirming this information. The system will automatically inform Novartis monitor for the site and the study team that the code has been broken.

It is the investigator's responsibility to ensure that there is a dependable procedure in place to allow access to the IRT/code break cards at any time in case of emergency. The investigator will provide:

- protocol number
- participant number

In addition, oral and written information to the participant must be provided on how to contact the investigator or his/ her backup in cases of emergency, or when he/she is unavailable, to ensure that un-blinding can be performed at any time.

In case of emergency code breaks, the respective participant is not eligible for joining the extension study anymore.

## 7 Informed consent procedures

Eligible participants may only be included in the study after providing (witnessed, where required by law or regulation), IRB/IEC-approved informed consent and assent, if applicable.

If applicable, in cases where the participants' representative(s) gives consent (if allowed according to local requirements), the participant must be informed about the study to the extent possible given his/her understanding. If the participant is capable of doing so, he/she must indicate agreement by personally signing and dating the written informed consent or assent document.

Informed consent must be obtained before conducting any study-specific procedures (e.g. all of the procedures described in the protocol). The process of obtaining informed consent must be documented in the participant source documents.

The Investigator or his/her representative will explain the nature of the study, including the risks and benefits, to the participant or their legally authorized representative and answer all questions regarding the study.

Participants must be informed that their participation is voluntary. Participants or their legally authorized representatives will be required to sign a statement of informed consent that meets the requirements of 21 CFR 50, local regulations, ICH guidelines, privacy and data protection requirements, where applicable, and the IRB/IEC or study center.

A copy of the ICF(s) must be provided to the participant or their legally authorized representative.

[figure not shown]
The medical record must include a statement that written informed consent was obtained before the participant was enrolled in the study and the date the written consent was obtained. The authorized person obtaining the informed consent must also sign the ICF.

Per [Section 4.6](#) during a Public Health emergency as declared by Local or Regional authorities (i.e. pandemic, epidemic or natural disaster), that may challenge the ability to obtain a standard written informed consent due to limits that prevent an on-site visit, the investigator may conduct the informed consent discussion remotely (e.g. telephone, videoconference) if allowable by local Health Authorities.

Guidance issued by local regulatory bodies on this aspect prevail and must be implemented and appropriately documented (e.g. the presence of an impartial witness, sign/dating separate ICFs by trial participant and person obtaining informed consent, etc.).

Novartis will provide to investigators in a separate document a proposed informed consent form that complies with the ICH GCP guidelines and regulatory requirements and is considered appropriate for this study. Any changes to the proposed consent form suggested by the investigator must be agreed by Novartis before submission to the IRB/IEC. Likewise, Novartis will also provide to investigators in separate documents proposed age-appropriate child assent forms.

Information about common side effects already known about the investigational drug can be found in the Investigator's Brochure (IB). This information will be included in the participant informed consent and assents and should be discussed with the participant during the study as needed. Any new information regarding the safety profile of the investigational drug that is identified between IB updates will be communicated as appropriate, for example, via an investigator notification or an aggregate safety finding. New information might require an update to the informed consent and then must be discussed with the participant.

This ICF will contain a separate section that addresses the use of remaining mandatory samples for optional additional research. The Investigator or authorized designee will explain to each participant the objectives of the additional research. Participants will be told that they are free to refuse to participate and may withdraw their consent at any time and for any reason during the storage period. A separate signature will be required to document a participant's agreement to allow any remaining specimens to be used for additional research. Participants who decline to participate in this optional additional research will document this.

- Parent/Guardian study consent including the subsections mentioned above.
- Child Assent for ages 6-11 years
- Adolescent Assent for ages 12-17 years
- As applicable, Pregnancy Outcomes Reporting Consent for female participants who took study treatment

If a minor participant reaches the age of legal majority in the course of the study, he/she/they must be re-consented as an adult.

Women of child bearing potential must be informed that taking the study treatment may involve unknown risks to the fetus if pregnancy were to occur during the study and agree that in order to participate in the study they must adhere to the basic (acceptable effective) contraception requirements.

[REDACTED]

A copy of the approved version of all consent/assent forms must be provided to Novartis after IRB/IEC approval.

Participants might be asked to complete an optional questionnaire to provide feedback on their clinical trial experience.

